Aim: To test the proof of principal that JNJ-39393406 promotes smoking cessation. We have developed, tested, and validated an innovative and efficient Phase 2a screening procedure that optimally combines the validity of randomized clinical trials with the practicality of lab- based medication studies. As detailed elsewhere (Perkins & Lerman 2014), it employs a within-subject, cross-over design comparing active versus placebo effects on quitting smoking to maximize statistical power without a large sample. We have demonstrated the sensitivity of this approach in identifying efficacy for biochemically-verified (CO) abstinence in all 3 of the first- line FDA-approved cessation medications, as well as its specificity in identifying lack of efficacy for abstinence in a medication known to not aid cessation. Using this procedure, we will evaluate effects of JNJ-39393406 vs. placebo on short-term smoking abstinence in smokers who already have a high interest

in quitting soon. We predict that, compared with placebo, JNJ-39393406 will increase days of abstinence, identifying initial evidence of efficacy for smoking cessation.

Our main dependent measure is days of very stringent biochemically validated (expired CO<5 ppm) 24-hr smoking abstinence, with post-quit withdrawal and cognitive function as secondary measures. Potential for adverse side-effects will be assessed at each visit. We hypothesize that the number of days of abstinence will be significantly greater for JNJ-39393406 vs. placebo.

Study Design and Methods

Random assignment: Upon entry into the study, subjects will be randomly assigned in double-blind fashion to medication order (active drug then placebo, or vice versa) within the cross-over design. We will use permuted-block randomization to assign subjects to these medication order conditions. The same order assignment will not be repeated more than 3 consecutive times, to prevent an imbalance in the sequence of these orders.

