Medication: Active JNJ-39393406 (50 mg tablets), abbreviated here “JNJ” (IND #122957) and matching placebo (both from Janssen Research and Development LLC) will be encapsulated by the WPIC Investigational Drug Service (IDS) research pharmacy. Staff and participants are blind to medication assignment by IDS (i.e. double blind). To start the dose run-up, participants will take one capsule of JNJ-39393406 (50 mg), or identically appearing placebo, once on day 1, incrementing by 50 mg daily to reach 200 mg by day 4. The full dose involves two capsules, each twice per day (100 mg b.i.d. for JNJ), in the a.m. and evening, over the remaining 7 days of that medication condition, including the 5-day practice quit period (Mon-Fri), when they will come to the lab each day to provide CO validation of quit status, plus provide self-reported withdrawal and possible adverse effects. One day will also include computerized test of cognitive processing (see below). One week of *ad lib* smoking follows the first quit attempt phase prior to the dose run-up week with the other condition, to allow separate 3-week tests of each in aiding smoking abstinence.

Procedure: Participation for each subject will be 6 weeks after randomization, involving two 3-week phases, one for each drug condition in this double-blind, crossover procedure. For each phase, visits occur on Mon and on Thurs of the first 2 weeks and Mon-Fri of the third week. CO is assessed upon arrival to each session, along with MNWS withdrawal. Each phase begins with a week of *ad libitum* smoking (baseline, week 1), with drug regimen started on Mon a.m. of week 2 while continuing to smoke (dose run-up). On week 3, they are instructed to try to abstain as of Sun am through the mid-day Fri visit, with CO assessments of quit status on Mon-Fri of week 3. On Mon of week 3, all completed testing of cognitive function (CPT). After Fri of week 3, all then *ad lib* smoke for at least a week to repeat this 3-week phase for the other condition: smoking without drug (i.e. washout; week 4), next dose run-up (week 5), and trying to quit during Mon-Fri (week 6).

Measures:

Smoking outcome. During the “quit week” (week 3) of each condition, the primary outcome of 24-hr abstinence is assessed daily on Mon-Fri by expired-air carbon monoxide (CO) <5 ppm.

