Secondary outcomes. Also examined daily are abstinence symptoms on the Minnesota Nicotine Withdrawal Scale (MNWS) (Hughes *et al.* 1991), with each item scored on a 0-100 VAS. In addition, we will assess the Penn Continuous Performance Task (CPT) assessing sustained attention (Kurtz *et al.*, 2001; Gur *et al.*, 2010) on Mon of each quit week. Also assessed daily (Mon-Fri) of the two “quit” weeks (weeks 3 and 6) are medication blinding and side-effects, rated on a 0 to 3 scale (none, mild, moderate, severe). Potential adverse effects will also be assessed by repeat of EKG and lab tests (see end of screening in Eligibility section below) on Fri of week 3 on each condition.

Eligibility Criteria

Randomized will be 60 dependent smokers aged ≥ 18 and < 66 (about 30 women, 30 men) with a high interest in quitting smoking (defined below), i.e. those shown in our prior research to be more sensitive to cessation medication efficacy. All subjects will be smokers with a high interest in quitting soon (within 3 months). Subjects also will be those who have smoked at least 10 cigarettes per day for at least 1 year, with no current use of non-tobacco nicotine products. To obtain 60 participants, we expect to screen about 80 male or female smokers, aged ≥ 18 and < 66 years, living in Allegheny or neighboring counties of the greater Pittsburgh metropolitan region, who do not have significant health problems. We will also assess the Fagerstrom Test of Nicotine Dependence (FTND; Heatherton *et al.* 1991) and other smoking characteristics, but will not select based on these factors. We selected these inclusion criteria because they approximately fit the current FDA-approved indications for smoking-cessation medications, and because we are interested in responses to this active compound, JNJ-39393406, among dependent smokers with an interest in quitting, those most likely to use such medications to help them quit smoking.

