Screening will also include assessment of alcohol use via the AUDIT (Saunders *et al.* 1993), as those with scores indicating dependence are excluded. Self-report of no more than 15 drinks/week and 3 drinks on any day in the past week are required. Those not ineligible at screening will receive a physical exam by study physician, including EKG, bloodwork to check liver and kidney function (CBC, etc.), illicit drug screen (other than THC), urine pregnancy test (women), and interview to assess history of psychiatric disorders, suicidal ideation, current major health problems (e.g. heart disease, diabetes) or contraindicated medications (e.g. fentanyl, cyclosporine, pimozide, quinidine).

Statistical Considerations

Analyses will be conducted using IBM SPSS 24.0. Preliminary analyses of variance (ANOVAs) examine effects of sex and of medication order between phases. The primary outcome, number of days abstinent per assessment week (range of 0-5 days), will be analyzed using paired t-tests. Medication condition (active JNJ, placebo) is the within-subjects factor. Generalized estimating equations (GEE) assesses differences between conditions for the secondary outcome of withdrawal, limited to only responses from days in which smoking abstinence is confirmed. Results of cognitive testing are to be examined using paired t-tests for the CPT. Medication condition is a within-subjects factor. Similar to analyses of withdrawal, to detect potential efficacy of conditions on cognitive testing unconfounded by recent smoking, cognitive responses will be analyzed only when CO<10 on both the JNJ and placebo testing sessions, as in prior research (e.g. Perkins, Karelitz, *et al.* 2013b).

References

Brunzell DH, McIntosh JM (2012) Alpha7 nicotinic acetylcholine receptors modulate motivation to self-administer nicotine: Implications for smoking and schizophrenia. *Neuropsychopharmacol.* **37**:1134-1143.

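### An abstinent day is defined by CO below 5 ppm, but nothing at entry checks that a participant's ordinary smoking CO lies above that level

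*Combined protocol and SAP*

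**What the plan says.** **Endpoint.** The Aim under Study Objectives states: "Our main dependent measure is days of very stringent biochemically validated (expired CO<5 ppm) 24-hr smoking abstinence". Measures repeats it: "the primary outcome of 24-hr abstinence is assessed daily on Mon-Fri by expired-air carbon monoxide (CO) <5 ppm". The cut-off is absolute. No change from the participant's own smoking level is required, and no accompanying report of not smoking is written into the definition.

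**Entry.** Eligibility Criteria requires a consumption level and duration: "Subjects also will be those who have smoked at least 10 cigarettes per day for at least 1 year". Nicotine dependence is measured along with related features, "and other smoking characteristics, but will not select based on these factors". The screening work-up is described as "Those not ineligible at screening will receive a physical exam by study physician, including EKG, bloodwork to check liver and kidney function", and continues with a drug screen, a pregnancy test and an interview. CO and cotinine are not mentioned.

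**CO while smoking.** Procedure says: "CO is assessed upon arrival to each session, along with MNWS withdrawal". Sessions fall on Monday and Thursday of the first two weeks of each phase, so week 1, which is ad lib and before any capsule, yields two readings per person. No eligibility or analysis rule refers to them. Randomisation takes place at study entry and the six weeks follow it, so week 1 comes after randomisation.

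**Analysis.** Statistical Considerations compares days abstinent (0 to 5) by paired t-test and restricts the withdrawal analysis to days of confirmed abstinence. It gives no alpha, power, effect size or standard deviation.

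**The concern.** An absolute threshold shows that someone has stopped smoking only if that person was above it while smoking. The plan measures the quantity that would show this but never requires it. A participant who smokes as usual with CO below 5 ppm would be scored abstinent on up to five days in each quit week.

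Three things follow:

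- The paired difference for that person is zero whatever the drug does, so the estimated effect shrinks.
- Mean days abstinent rise in both conditions, which matters if the absolute level is reported or compared with other medications tested by the same procedure.
- The withdrawal analysis, meant to describe abstinent days, takes in smoking days, and it draws more days from such a participant than from others.

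The trial is a small screening study intended to give initial evidence of efficacy, so a diluted null result is the error to guard against.

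**Working it through.** **No figure to reproduce.** The plan gives 60 randomised participants but no sample-size calculation. What follows is illustration, with assumptions marked.

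**1. Dilution of the effect.** Let *f* be the share of participants whose CO is always below 5 ppm (assumed; not in the documents). They score 5 of 5 in both conditions, so their difference is 0. For the rest, let the mean difference be δ and its standard deviation 1, so that δ is in SD units. Then:

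- mean difference = (1 − f)δ
- variance = (1 − f) + f(1 − f)δ²
- standardised effect = mean ÷ √variance

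Assume a two-sided paired t-test at alpha 0.05 with 80% power at n = 60 when f = 0. Solving the noncentral t gives δ = 0.368. For f = 5%: mean 0.95 × 0.3677 = 0.349; variance 0.95 + 0.0475 × 0.1352 = 0.956; standardised effect 0.349 ÷ 0.978 = 0.357.

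| f | Participants of 60 | Standardised effect | Power | n to regain 80% | Maximum added mean days per condition (5f) |
|---|---|---|---|---|---|
| 0 | 0 | 0.368 | 80.0% | 60 | 0 |
| 2% | 1.2 | 0.364 | 79.1% | 62 | 0.10 |
| 5% | 3 | 0.357 | 77.7% | 64 | 0.25 |
| 10% | 6 | 0.347 | 75.2% | 68 | 0.50 |

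The last column assumes these participants would otherwise have scored 0, so it is an upper limit. On the raw scale, an assumed 0.5-day benefit becomes 0.5 × 0.98 = 0.49 day at 2% and 0.5 × 0.90 = 0.45 day at 10%.

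**2. Share of the withdrawal data.** Assume f = 5% and that the other participants average 1 to 2 abstinent days per quit week. The 5% supply 0.05 × 5 = 0.25 day per participant enrolled; the others supply 0.95 × 1 = 0.95 to 0.95 × 2 = 1.90. The share is 0.25 ÷ 1.20 = 21% down to 0.25 ÷ 2.15 = 12%.

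**3. Can a smoker at the entry minimum be below 5 ppm?** All kinetic inputs here are assumed: a one-compartment steady state, 10 cigarettes at equal spacing from 07:00 over a 16-hour day, background 1 ppm, and half-life 3 h awake with 5 h asleep, or 5 h awake with 8 h asleep.

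| CO rise per cigarette | 9 a.m. | Noon |
|---|---|---|
| 1.5 ppm | 4.0 and 5.7 | 4.9 and 6.7 |
| 2 ppm | 5.0 and 7.3 | 6.2 and 8.6 |
| 3 to 4 ppm | about 7 to 13.5 | all above 5 |

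So a value below 5 ppm is possible at the entry minimum, but only at the low-rise, fast-clearance corner. Changing the spacing of cigarettes moves the values, so this shows possibility and not frequency.

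**4. What a high floor would do.** Across the same eight combinations (rises of 1.5, 2, 3 and 4 ppm by two half-life pairs), a truthful 10-a-day smoker is below 10 ppm in 6 of 8 at 9 a.m. and 5 of 8 at noon.

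**The case against.** The strongest case against is that the problem is rare and mild. A score of 5 of 5 in both weeks needs ten readings under 5 ppm from a continuing smoker who was chosen for high interest in quitting and told to abstain. The cut-off was deliberately set low. The only visit time the documents hint at is midday on Friday, when CO would usually be higher than early in the morning. Each participant is their own control, so the error is the same in both conditions. At 2% to 5% prevalence, power falls by one to two percentage points. All of this stands, and it limits the weight of the point. It does not supply the missing check.

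A reader may also say that 24-hour abstinence implies a report of not smoking. It may, but no such rule is written, and Measures has CO alone deciding the day.

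Four stronger readings are tempting and should not be drawn:

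- **That the trial is biased toward the drug.** It is not on this account. These participants contribute zero difference, so the effect moves toward the null.
- **That many participants are affected, or that people overstate smoking to qualify.** The documents give no ad lib CO distribution and do not say how consumption is verified. Both would be guesses.
- **That 10 ppm is the right entry floor, since the cognitive analysis uses CO below 10.** That filter concerns recent smoking before a test session. It is not a basis for entry, and item 4 of the working shows such a floor could exclude many genuine 10-a-day smokers.
- **That smokers just above 5 ppm who cut down slightly belong to this point.** Whether CO below 5 separates abstinence from reduction is a question about the endpoint. An entry check at 5 ppm would not settle it.

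**Conclusion.** The gap is real on the text: an absolute CO endpoint, consumption-based entry with no biochemical confirmation, and ad lib CO readings that no rule uses. As written, the plan can count a participant already under 5 ppm as abstinent in both conditions.

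Its size is modest and uncertain. If 80% power is assumed, it would be about 79%, 78% or 75% with 2%, 5% or 10% such participants. These figures rest on the assumed alpha, the assumed baseline power, and participants who are always below the threshold. The true prevalence is unknown and may be near zero. This is a worthwhile, inexpensive improvement; it does not undermine the design.

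**What to change.** **Eligibility Criteria.** Add an expired CO reading taken during ad lib smoking, before randomisation, that must not already meet the endpoint: at minimum, CO of 5 ppm or more. If the sponsor wants a wider margin, such as 10 ppm, it should set it from its own ad lib CO data and state the screen failures expected.

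**Statistical Considerations.** For participants already randomised, prespecify a sensitivity analysis of the primary paired comparison that leaves out anyone with a week-1 CO below 5 ppm. Both week-1 readings precede the first capsule, so the exclusion cannot depend on the drug. Week 4 should not be used in the same way, because it follows the first treatment period.

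**Cost.** One breath reading at screening with equipment already in use, some additional screen failures among lighter smokers beyond the roughly 80 people now planned for screening, and a slightly smaller n in the sensitivity analysis. The week-1 readings are already scheduled.

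### Does the primary paired t-test need a stated analysis set and a different model for quit weeks that are never reached?

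*Combined protocol and SAP*

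**What the plan says.** Under Random assignment (Study Design and Methods): "Upon entry into the study, subjects will be randomly assigned in double-blind fashion to medication order". Under Procedure: "Participation for each subject will be 6 weeks after randomization, involving two 3-week phases". The quit weeks are weeks 3 and 6, so both primary values exist only for someone who stays to the end.

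The outcome is defined in Study Objectives as "days of very stringent biochemically validated (expired CO<5 ppm) 24-hr smoking abstinence", and under Measures: "the primary outcome of 24-hr abstinence is assessed daily on Mon-Fri by expired-air carbon monoxide (CO) <5 ppm". The test, in Statistical Considerations, is: "The primary outcome, number of days abstinent per assessment week (range of 0-5 days), will be analyzed using paired t-tests".

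The same section does say which data enter the two secondary analyses. Withdrawal is "limited to only responses from days in which smoking abstinence is confirmed". For the continuous performance task, "cognitive responses will be analyzed only when CO<10 on both the JNJ and placebo testing sessions". Nothing comparable is written for the primary outcome. The only attrition figure, about 80 screened to obtain 60 (Eligibility Criteria), concerns the time before randomisation.

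**The concern.** A paired t-test needs a difference for each person. Someone who leaves after week 3 has none, unless an analyst assigns a value to the missing week. The plan mentions neither course, so two readings are possible. One analyses complete pairs. The other treats an unreached week as having no validated days, scores it 0 and keeps all 60.

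If loss differs between the two medication orders, the readings can give different estimates, and a choice made with the outcomes in view would be an analyst's freedom in a small efficacy screen. Complete pairs also discard observed week-3 data in a design chosen "to maximize statistical power without a large sample". The natural remedy would be a linear mixed model (treatment, period, sequence, random participant) as the primary analysis, with explicit rules for missing weeks.

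**Working it through.** **Inputs.** From the documents: 60 randomised, two quit weeks, outcome 0-5 days, paired t-test. There is no planned power figure to reproduce, because alpha, power, effect size, SD and drop-out are not given. Assumed: two-sided alpha 0.05, 30 people per order, no true drug effect, no period effect, and rounded 0-5 day counts with mean 1.68, SD 1.48, 29% at zero and paired-difference SD 1.54. All loss rates are assumed and written active first/placebo first. *Shift* means the estimate minus the no-loss estimate in the same simulated trials.

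**1. Precision.** SE without loss = 1.54/√60 = 0.20 days. The difference detectable with 80% power (noncentral t) is 0.368 SD with 60 pairs, 0.388 with 54 and 0.413 with 48. The SE ratios √(60/n) are 1.054 and 1.118.

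**2. Complete pairs, loss only among week-3 non-abstainers.** Each order has about 0.29 × 30 = 8.7 such people. In the active-first order they have 0 active days and, on average, some placebo days. Losing them raises the estimate. In the other order the effect is reversed, so equal loss cancels.

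| Loss | Expected number lost | Shift (days) | Type I error |
|---|---|---|---|
| 30/30 | 8.7 × 0.6 = 5.2 | 0.00 | about 5% |
| 30/10 | 8.7 × 0.4 = 3.5 | +0.03 | 4.9-5.3% |
| 50/10 | 8.7 × 0.6 = 5.2 | +0.055 | 5.4% to about 6% |
| 80/0 | 8.7 × 0.8 = 7.0 | +0.115 | 8.1-8.5% |

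At 50/10 the shift is 0.055/0.20, about a quarter of an SE. Reversing the orders reverses the sign.

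**3. The two readings, loss unrelated to outcome.** Complete pairs: shift 0.00, type I error about 5%. Scoring the unreached week 0: shift = ½ × (difference in loss between orders) × mean days. At 30/10 this is ½ × 0.20 × 1.68 = +0.168, and the simulated type I error is about 11%. At 20/20 it is 0.00. So the readings separate only when loss is unequal by order, and here the default reading is the sound one.

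**4. The mixed model as a replacement.** Take the version that counts days without a CO<5 reading in a started phase as not abstinent and leaves never-started phases missing.

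| Setting | Complete pairs | Mixed model with that rule |
|---|---|---|
| Non-abstainers leave, 80/0, all before phase-2 dosing | +0.115 | -0.008 |
| Same, all after phase-2 dosing starts | +0.115 | +0.103 |
| Random 30/10, half after dosing starts | 0.00; 4-5% | +0.10; 7.5-8.5% |
| Random 30/10, all after dosing starts | 0.00; 4-5% | +0.17; 11.5-11.6% |
| Random 20/10, all after dosing starts | 0.00; 5.0% | +0.08; 6.4% |
| Random loss in phase 1, 20/5 | 0.00; 4.7% | -0.07; 6.1% |

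The rule helps only when loss falls before phase-2 dosing and depends on the week-3 result. If every unreached week is left missing instead, the mixed model stays within 0.01 day in the outcome-related settings of step 2. Its gain in precision is small: at 20% random loss the SE is 0.217 against 0.223, a ratio of 0.973. At 80/0 its SE is slightly larger than that of complete pairs (0.218 against 0.213).

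**The case for a change.** The strongest case for acting is that the silence is real and confined to the primary outcome, that nothing suggests a rule was blacked out, and that the two readings can give about 5% or about 11% type I error on the same data. A sentence naming the set would cost nothing. Appealing to a convention that missing means smoking does not settle it either, because scoring a phase that never began charges a failure to a treatment the person did not receive.

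Most of that stands as description. It does not show that the plan's test is unsound. Scoring an unreached week 0 needs an imputation step that the plan does not mention, whereas complete pairs are what the named test does with the data as they come. A result based on complete pairs also shows itself in the degrees of freedom. Nothing in the documents indicates that the choice was left until after unblinding. A sentence naming the set would be tidy, but it would record the default and not alter the analysis.

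One limit on the defence is that the calculations assume no period effect. After random 30/10 loss, 21 active-first and 27 placebo-first pairs remain. A period effect of π days would then move the complete-pairs estimate by (27 - 21)/48 × π = 0.125π, or about 0.06 days for a half-day effect. The preliminary ANOVA on medication order is where such an effect would show.

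**Conclusion.** No change follows. The plan leaves out a detail that an analyst fills sensibly: complete pairs for the t-test, and a day without a validated reading not counted as abstinent. On that reading the primary result is unbiased when loss is equal by order or unrelated to outcome. It moves by at most about a quarter of an SE when non-abstainers leave at rates as unequal as 50%/10%. Type I error exceeds 8% only at 80%/0%. Replacing the primary test is a debatable trade: one version can be worse than the t-test, and the version that holds up gains under 3% in SE.

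This rests on assumed loss rates, an assumed day-count distribution and no period effect, since the documents supply none of these. A large, lopsided loss of non-abstainers from one order would weaken the conclusion.

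### The primary paired t-test ignores period in a two-period cross-over: some power is lost, and the estimate shifts if completers are unequal by order

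*Combined protocol and SAP*

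**What the plan says.** Study Design and Methods (Random assignment) sets up an AB/BA cross-over: "subjects will be randomly assigned in double-blind fashion to medication order (active drug then placebo, or vice versa) within the cross-over design". The allocation is restricted: "The same order assignment will not be repeated more than 3 consecutive times, to prevent an imbalance in the sequence of these orders". Under Procedure, after the first quit week and a period of smoking without drug, participants go on "to repeat this 3-week phase for the other condition". The two quit attempts fall in weeks 3 and 6.

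Statistical Considerations tests the primary outcome as follows: "number of days abstinent per assessment week (range of 0-5 days), will be analyzed using paired t-tests". It adds: "Medication condition (active JNJ, placebo) is the within-subjects factor". Order appears once, before that: "Preliminary analyses of variance (ANOVAs) examine effects of sex and of medication order between phases". The model for this ANOVA is not given, and nothing says how its result bears on the primary test.

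The cognitive outcome has the same form: "Results of cognitive testing are to be examined using paired t-tests for the CPT". It is further restricted: "cognitive responses will be analyzed only when CO<10 on both the JNJ and placebo testing sessions".

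**The concern.** A second attempt to quit within three weeks of the first need not go like the first. Practice, discouragement or a change in motivation could each move days abstinent. In an AB/BA design such a period effect pushes the active-minus-placebo difference one way in one order and the opposite way in the other. A paired t-test pools the two orders as one sample. The period effect then does one or both of two things:

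- It inflates the variance that the test uses, at any split of completers.
- It leaves a residue in the mean when the two orders have different numbers of completers.

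The cross-over was chosen for its power in a small sample, and the randomisation takes care to balance order, but the stated primary test makes no use of order. In a proof-of-principle screen, a test that is conservative for no benefit raises the chance of passing over an active compound.

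The CPT is more exposed. It is a repeated task, so a practice effect is plausible, and the CO<10 rule removes people after randomisation.

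**Working it through.** **Inputs.** From the documents: 60 randomised, two orders, paired t-test, medication as the only factor. Not stated, so assumed: 30 per order, two-sided 5% level, SD of the within-person difference (within order) 1.5 days, drug effect δ = 0.55 day, and period effect π (second attempt minus first) from 0.25 to 1.0 day. The plan states no power figure to reproduce.

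**Model.** Let n1 be completers given active first, n2 those given placebo first, and N = n1 + n2. The active-minus-placebo difference has mean δ − π in the first group and δ + π in the second. Hence:

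- Mean of the pooled differences: δ + π(n2 − n1)/N.
- Expected variance used by the paired t-test: SD² + 4·n1·n2·π²/[N(N − 1)]. At 30/30 this is SD² + π²·60/59, or about SD² + π².
- True variance of the pooled mean: SD²/N. The test therefore divides by a standard error that is too large.

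**Paired-t rejection probability.** The mean is normal with variance SD²/N. Independently, the sum of squares over SD² is noncentral chi-square with N − 1 df and noncentrality 4·n1·n2·π²/(N·SD²). At 30/30 and π = 0.75 the noncentrality is 4·900·0.5625/(60·2.25) = 15. Integrating numerically over the mean gives the exact power.

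**Adjusted test.** Half the difference between the two orders' mean period differences has standard error (SD/2)·√(1/n1 + 1/n2), with N − 2 df. At 30/30 this is 1.5/√60 = 0.194, the noncentrality is 0.55/0.194 = 2.84, and power on 58 df is 79.8% whatever π is.

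**Equal completers, 30/30**

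| Period effect (days) | Paired-t power | Adjusted power | Paired-t type I error | Interval too wide by, √(1 + π²/SD²) − 1 |
|---|---|---|---|---|
| 0.25 | 79.0% | 79.8% | 4.7% | 1% |
| 0.5 | 76.6% | 79.8% | 3.9% | 5% |
| 0.75 | 72.5% | 79.8% | 2.9% | 12% |
| 1.0 | 66.6% | 79.8% | 1.9% | 20% |

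With the effect rescaled to keep 80% adjusted power, a 0.5-day period effect gives paired-t power of 73% if SD is 1.0 and 78% if SD is 2.0. At 0.25 day the figures are 78% and 80%.

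A simulation with outcomes bounded at 0–5 days gave the same pattern. At a period effect of about 0.69 day and SD of about 1.7, type I error was 3.4% paired against 5.0% adjusted. Power was 47% against 53% for an effect of 0.46 day.

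**Unequal completers, six lost from 60** (active first / placebo first)

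| Split | π = 0.25: shift, power | π = 0.75: shift, power | Adjusted power |
|---|---|---|---|
| 28/26 | −0.01 day, 73% | −0.03 day, 62% | 75% |
| 26/28 | +0.01 day, 76% | +0.03 day, 72% | 75% |
| 30/24 | −0.03 day, 70% | −0.08 day, 52% | 75% |
| 24/30 | +0.03 day, 79% | +0.08 day, 80% | 75% |

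For example, 30/24 at π = 0.75 shifts the estimate by 0.75·(24 − 30)/54 = −0.08 day. The 80% at 24/30 is partly upward bias. Type I error stays below 5% in all of these cases. At a wider split of 30/22 with SD 2.0 it is 5.2% to 5.4%, so still close to nominal.

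If dropout is unrelated to order, six dropouts from 30/30 leave a mean imbalance of 1.8 people. The extreme split has a 2.4% chance in either direction together, or 1.2% each way.

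**CPT.** If 40, 30 or 20 of 60 pass the CO<10 rule at random with respect to order, the average absolute shift is 7%, 10% or 14% of the practice effect. The chance of a shift of at least 20% of it is 5%, 20% or 41%.

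**The case against.** The case for leaving the plan alone has four parts.

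1. **No invalid test is shown.** Order is randomised in restricted blocks, so balance is expected. With balance the test is unbiased and conservative. This stands. The point is about efficiency and the accuracy of the estimate, not false positives.

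2. **The larger losses need large period effects.** Power of 72% or 67% requires a period effect above the assumed drug effect of 0.55 day. At 0.25 and 0.5 day the loss is about 1 and 3 points. This stands, and nothing in the documents says how large the period effect is.

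3. **Random dropout adds little beyond the variance inflation.** Averaged over six random dropouts, the shift is zero in expectation. Its mean absolute size is 0.008, 0.016 and 0.025 day at period effects of 0.25, 0.5 and 0.75 day. Average power is 74.4%, 71.7% and 67.1% against 75.2% adjusted, and a balanced 27/27 at 0.75 day gives almost the same, 67.3%. This also stands. The shift matters mainly if the realised split is uneven, which adjustment would cover at almost no cost.

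4. **The preliminary ANOVA may already do the job.** If it crosses medication with order, its interaction is the period effect and its medication term is period-adjusted. That is possible, but the plan does not say so and names the paired t-test for the primary outcome. Examining order is not the same as adjusting for it.

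The CPT figures concern a secondary outcome and an unknown practice effect. They support using the same method there but add no weight to the primary point.

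**Conclusion.** The concern holds. The stated primary test does not remove a difference between the first and second quit attempt, and the order ANOVA is given no role that would.

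Under the assumptions above, the likely cost is modest: about 1 to 3 points of power for period effects up to 0.5 day, and 7 to 13 points at 0.75 to 1.0 day. A smaller SD makes it worse (about 7 points at 0.5 day if SD is 1.0). The estimate shifts by the period effect times the proportional imbalance in completers, typically a few hundredths of a day with random dropout and more if dropout depends on order. The direction of the shift cannot be known in advance.

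The change is worth making because the gain is real whenever a period effect exists and the cost is close to nil when it does not. Confidence in the size is moderate, since every quantity behind it is assumed.

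**What to change.** State in Statistical Considerations that the primary analysis is the period-adjusted medication effect. Either of these will do:

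- a two-sample t-test comparing period differences between the two orders; or
- equivalently for complete pairs, a model with medication, period and sequence as fixed effects and a random participant effect.

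If the preliminary ANOVA already crosses medication with order, say so and name its medication term (unweighted means) as the primary test. Apply the same adjustment to the CPT and report how many participants are retained in each order. Report the order term descriptively and do not let it decide which primary test is used. Period adjustment does not deal with carry-over, which is a separate matter.

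The cost is a change of wording and one degree of freedom, with no new data. With no period effect, power is 79.8% either way at 30/30. It falls by under 0.1 point at 28/26, by about 0.6 point at 30/24 (75.3% to 74.8% as rounded), and by about 1 point at 31/23.
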